5.3 Statistical Methods for Safety Analyses

The analysis set for all safety analyses is defined in Section 2.1. Baseline will be defined as the last measurement prior to exposure to study lenses. For biomicroscopy data, baseline will be defined as Visit 2 for Period 1 and Visit 5 for Period 2. Safety variables will be summarized descriptively.

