## 8.2 Exclusion Criteria

Subjects fulfilling **any** of the following criteria are not eligible for participation in this study.

1. Any anterior segment infection, inflammation, or abnormality or disease (including systemic) that contraindicates contact lens wear, as determined by the investigator
2. Any use of systemic or ocular medications for which contact lens wear could be contraindicated, as determined by the investigator.
3. History of refractive surgery or irregular cornea in either eye.
4. Ocular or intraocular surgery (excluding placement of punctal plugs) within the previous 12 months.
5. Biomicroscopy findings at screening that are moderate (Grade 3) or higher and/or corneal vascularization that is mild (Grade 2) or higher; presence of corneal infiltrates.
6. Current or history of pathologically dry eye in either eye that, in the opinion of the investigator, would preclude contact lens wear.
7. Current or history of herpetic keratitis in either eye.
8. Eye injury in either eye within twelve weeks immediately prior to enrollment for this trial.

[figure not shown]
	
[name]

Indication for use and intended purpose in the current study
	
The investigational LID226397 contact lenses are indicated for the optical correction of ametropia (myopia or hyperopia, with astigmatism) in persons with non-diseased eyes.
 
The lenses are intended for daily wear (less than 24 hours while awake), with removal for cleaning and disinfection (chemical, not heat) prior to reinsertion, or for disposal, as recommended by the eye care professional. [REDACTED] [REDACTED] [REDACTED]

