## 10 STUDY PROCEDURES AND ASSESSMENTS

Subjects will be expected to attend 7 office visits, as shown below.

Visit #	Visit Type	Lens (Period)	Visit Window
Visit 1	Screening/ Baseline	N/A	N/A
Visit 2	Dispense Lens 1	Lens 1 (Period 1)	3 - 4 days after Visit 1 (Washout period with habitual spectacles only after Visit 1)
Visit 3	Week 1 Follow-up Lens 1	Lens 1 (Period 1)	7 -0/+ 1 days after Visit 2
Visit 4	Week 2 Follow- up Lens 1	Lens 1 (Period 1)	7 -0/+ 1 days after Visit 3

Visit #	Visit Type	Lens (Period)	Visit Window
Visit 5	Dispense Lens 2	Lens 2 (Period 2)	2 (at least 48 hours) - 4 days after Visit 4 (Washout period with habitual spectacles only after Visit 4)
Visit 6	Week 1 Follow-up Lens 2	Lens 2 (Period 2)	7 -0/+ 1 days after Visit 5
Visit 7	Week 2 Follow-up Lens 2 /Exit	Lens 2 (Period 2)	7 -0/+ 1 days after Visit 6

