### ***Significant Nonserious Adverse Events***

A significant nonserious AE is a device-related, nonsight threatening adverse event that warrants discontinuation of any contact lens wear for greater than or equal to 2 weeks. In addition, the investigator must report any occurrence of the following as a Significant Nonserious Adverse Event:

- Peripheral nonprogressive noninfectious ulcers
- All symptomatic corneal infiltrative events
- Corneal staining score greater than or equal to grade 3 (Refer to MOP for grading scales)
- Temporary vision loss as defined by loss of 2 or more lines of BCVA (e.g., with manifest refraction or habitual correction) from enrollment visit that persists for 2 or more weeks
- Neovascularization score greater than or equal to grade 2 (Refer to MOP for grading scales)

*The above events are based on the categories provided in the ISO 11980 and the US FDA Premarket Notification (510(k)) Guidance Document for Daily Wear Contact Lenses.*

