## **12.6 Safety Analyses**

The safety endpoints are:

- AEs
- Biomicroscopy findings
- Device Deficiencies

There are no safety hypotheses planned in this study. The focus of the safety analysis will be a comprehensive descriptive assessment of occurrence of adverse events as well as the other listed parameters.

All AEs occurring from the time a subject signs informed consent to study exit will be accounted for in the reporting. Safety analyses will be conducted using the safety analysis set on a treatment-emergent basis. Descriptive summaries (frequencies and percentages) for ocular and nonocular AEs will be presented by Medical Dictionary for Regulatory Activities Preferred Terms. AEs leading to study discontinuation and SAEs will be identified. Individual subject listings will be provided, as necessary.

Individual subject listings will be provided for AEs that occur after signing informed consent but prior to exposure to IP.

Each biomicroscopy parameter will be tabulated by its grade. For each biomicroscopy parameter, frequencies and percentages of eyes that experience an increase of  $\geq 2$  grades from baseline (last assessment prior to study lens exposure) to any subsequent visit within the same period will be presented. A supportive listing will be generated which will include all biomicroscopy data from all visits within the same period for those eyes experiencing the increase.

Two listings for device deficiencies, prior to exposure to study contact lenses and treatment-emergent, will be provided. Additionally, each device deficiency category will be tabulated.

No inferential testing will be conducted for the safety analyses.

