5.3.2 Biomicroscopy Findings

[figure not shown]
The following tables and supportive listings will be provided:

- Frequency and Percentage for Biomicroscopy Findings by Visit
- Incidence of Increased Severity by 2 or More Grades in Biomicroscopy Findings
- Listing of Subjects With Other Biomicroscopy Findings
- Listing of Subjects With Conjunctival Compression/Indentation or Chemosis
- Listing of Subjects With Increased Severity by 2 or More Grades in Biomicroscopy Findings
- Listing of Subjects with Infiltrates

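### A biomicroscopy rise that first reaches 2 grades at Visit 5 is counted under neither lens in the increase table and is not listed as an increase

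*SAP*

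**What the plan says.** SAP 5.3 fixes the reference exam for each period: "For biomicroscopy data, baseline will be defined as Visit 2 for Period 1 and Visit 5 for Period 2". Protocol 12.6 defines the measure as the number and percentage of eyes that worsen by at least 2 grades "from baseline (last assessment prior to study lens exposure) to any subsequent visit within the same period will be presented". It limits the supportive listing to eyes with such an increase and to visits in the same period. SAP 5.3.2 plans the matching table and listing.

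The visit table in Protocol 10 places Visit 5 in Period 2, as the dispensing visit for the second lens, and schedules it "2 (at least 48 hours) - 4 days after Visit 4", with spectacles only in between. Biomicroscopy is scheduled at every visit, including Visit 5, and is required at unscheduled visits (Protocol 10.3).

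Visit 5 grades have other uses. SAP 5.3.2 plans a table titled "Frequency and Percentage for Biomicroscopy Findings by Visit" and listings of infiltrates, of compression or chemosis, and of other findings. None of these depends on a 2-grade rise.

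**The concern.** Visit 5 has two roles. It is the natural starting point for the second lens, and it is also the last scheduled look at the eye after the first lens. The increase analysis uses only the first role. A change that becomes visible shortly after the first lens is stopped is absorbed into the next period's starting value and is never compared with Visit 2.

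SAP 5.3.1 handles adverse events differently. Events arising in the washout form a separate between-treatment class with its own listings. Biomicroscopy change has no such category. Biomicroscopy is one of three safety endpoints, and the SAP aims at a comprehensive description of safety, so a reader of the increase table would expect every rise of that size either to be counted or to be shown somewhere as a rise.

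**Working it through.** The plan gives no rate or sample-size figure for this measure, so there is nothing to reproduce. The check applies the stated rule to all possible grade patterns.

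**Inputs.** Baselines are Visits 2 and 5 (SAP 5.3). Outcome visits are those later in the same period (Protocol 12.6), which gives Visits 3 and 4 for Period 1 and Visits 6 and 7 for Period 2 (Protocol 10). The grading scale is in the Manual of Procedures, which is not available here. The documents name Grade 2 as mild and Grade 3 as moderate. I assume a scale of 0–4 and repeat the check on 0–3.

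**Rule.** Let g2 and g5 be the grades at Visits 2 and 5, p1 the higher grade of Visits 3 and 4, and p2 the higher grade of Visits 6 and 7.
- Counted under the Period 1 lens if p1 − g2 ≥ 2.
- Counted under the Period 2 lens if p2 − g5 ≥ 2.
- The difference g5 − g2 is never formed.

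**Patterns in question.** These have g5 − g2 ≥ 2 and p1 − g2 < 2.
- Scale 0–4: g2 = 0 gives 3 values of g5 × 2 of p1 = 6; g2 = 1 gives 2 × 3 = 6; g2 = 2 gives 1 × 4 = 4. The total is 16, and with 5 values of p2 it is 16 × 5 = 80 patterns. Counted under Period 1: 0 of 80. Counted under Period 2: 2 of 80, both with g5 = 2 and p2 = 4. These two count because of a further rise on the second lens, not because of the rise seen at Visit 5.
- Scale 0–3: (2 × 2 + 1 × 3) × 4 = 28 patterns. Counted under Period 1: 0 of 28. Counted under Period 2: 0 of 28.

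These are counts of possible patterns, not probabilities. They show only that the omission follows from the rule whichever of the two scales applies.

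**Example.** Bulbar hyperemia is Grade 0 at Visit 2, 1 at Visit 4, 2 at Visit 5 and 2 at Visit 6. Period 1 change: 1 − 0 = 1. Period 2 change: 2 − 2 = 0. Visit 5 against Visit 2: 2 − 0 = 2. The eye is absent from the increase table and its listing.

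**Do other outputs show it?**
- The by-visit table shows the Grade 2 but, as titled, not that this eye has changed from Visit 2.
- A change that the investigator judges clinically relevant is reported as an adverse event (Protocol 11.2). If its onset falls in the washout, SAP 5.3.1 lists it as between-treatment and leaves it out of the treatment-emergent incidence tables.
- Two parameters have a mandatory route under Protocol 11.1: "Corneal staining score greater than or equal to grade 3", and neovascularization of Grade 2 or higher. A rise from 0 to 2 in hyperemia, or in corneal staining, has none.
- For an unscheduled exam between Visits 4 and 5, the visible text names no period. If the exam is treated as washout, the same gap applies.

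**The case against.** A period-specific baseline after a washout is a sound choice for a crossover, and the protocol and SAP apply it consistently. Rises already present at Visit 3 or 4 count under the first lens, so what escapes must first reach 2 grades after that lens has been stopped. Safety is descriptive, with no testing and no success criterion. All of this stands, and it is why the point is minor.

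A reader might infer more than the documents support:
- *That the Visit 5 exam has no use except as a baseline.* It also feeds the by-visit table, three kinds of listing and adverse event reporting.
- *That worsening on the second lens is hidden.* A raised Visit 5 grade does raise the bar, since the grade needed is g5 + 2. On an assumed 0–4 scale an eye at Grade 3 at Visit 5 cannot be flagged. However, the Period 2 grades stay visible by visit, and corneal staining of Grade 3 or higher must be reported as a significant nonserious event.
- *That the rule can only lose events.* With grades 1 at Visit 2, 0 at Visit 5 and 2 at Visit 6, the Visit 5 baseline gives 2 − 0 = 2 (counted), whereas a Visit 2 baseline gives 2 − 1 = 1 (not counted).
- *That one lens is favored.* Sequences are allocated 1:1 and both lenses face the same rule. The documents give no reason to expect different residual reactions.

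**Conclusion.** The point holds for one output, the table and listing of rises of 2 or more grades. There, a rise from Visit 2 first reaching that size at Visit 5, or at an unscheduled washout exam, counts under neither lens and is not listed as an increase. It is a possible small under-count, confined to changes first appearing in the 2 to 4 days after Visit 4. The documents give no rates from which to compute how many eyes are affected.

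The conclusion assumes that the Visit 5 baseline exam precedes insertion of the second lens, as the definition of baseline implies, and that no redacted text in the SAP or rule in the Manual of Procedures already assigns washout exams. It does not depend on the length of the grading scale. It does not justify moving the second lens to a Visit 2 baseline, which would mix carry-over from the first lens into the second.

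**What to change.** Leave the Visit 2 and Visit 5 baselines and the main increase table as they are. In SAP 5.3.2 add one supportive row and one listing, labelled between-treatment to match the adverse event classes in SAP 5.3.1. They would cover eyes whose grade at the pre-insertion Visit 5 exam, or at an unscheduled exam in the washout, is 2 or more grades above Visit 2. Show them by the lens worn in Period 1, and include the later Period 2 grades in the listing. State in SAP 5.3 that unscheduled exams between Visits 4 and 5 belong to this category.

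The cost is a few lines of SAP text and a little programming. The scheduled exams are already planned, and no error rate is affected. One limitation follows from the design: Period 2 ends at Visit 7 and has no matching post-washout exam. The row must therefore be shown separately and not added to the main Period 1 count.

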5.3.1 Adverse Events

The applicable definition of an AE is in the study protocol. All AEs occurring from when a subject signs informed consent to the time of their study exit will be accounted for in the reporting.

Presentation of AEs will be separated into pre-treatment AEs, between-treatment AEs, and treatment-emergent AEs as defined below:

- Pre-treatment: an event that occurs after signing informed consent but prior to exposure to study lenses

- Between-treatment: an event that occurs one day after last exposure to Period 1 study lenses but prior to exposure of Period 2 study lenses.
- Treatment-emergent: an event that occurs from exposure to Period 1 study lenses until subject exits from the study, excluding those classified as between-treatment

The following tables and supportive listings will be provided:

- Incidence of All Ocular Treatment-Emergent Adverse Events
- Incidence of Ocular Serious Treatment-Emergent Adverse Events
- Incidence of Ocular Significant Nonserious Treatment-Emergent Adverse Events
- Incidence of All Nonocular Treatment-Emergent Adverse Events
- Incidence of Nonocular Serious Treatment-Emergent Adverse Events
- Listing of All Ocular Treatment-Emergent Adverse Events
- Listing of All Nonocular Treatment-Emergent Adverse Events
- Listing of All Ocular Pre-Treatment Adverse Events
- Listing of All Nonocular Pre-Treatment Adverse Events
- Listing of All Ocular Between-Treatment Adverse Events
- Listing of All Nonocular Between-Treatment Adverse Events

5.3.2 Biomicroscopy Findings

[figure not shown]
The following tables and supportive listings will be provided:

- Frequency and Percentage for Biomicroscopy Findings by Visit
- Incidence of Increased Severity by 2 or More Grades in Biomicroscopy Findings
- Listing of Subjects With Other Biomicroscopy Findings
- Listing of Subjects With Conjunctival Compression/Indentation or Chemosis
- Listing of Subjects With Increased Severity by 2 or More Grades in Biomicroscopy Findings
- Listing of Subjects with Infiltrates

5.3.3 Device Deficiencies

[figure not shown]
The following tables and supportive listings will be provided:

[figure not shown]
- Frequency of Treatment-Emergent Device Deficiencies
- Listing of Treatment-Emergent Device Deficiencies
- Listing of Device Deficiencies Prior To Treatment Exposure

[figure not shown]

8 REFERENCES

Not applicable.

10 APPENDIX

[figure not shown]
Table 10-1 Schedule of Study Procedures and Assessments

| Procedure/ Assessment | Pre- screening | Visit 1 Screening/ Baseline/ Trial fit | Lens 1 (Period 1) | | | Lens 2 (Period 2) | | | Early Exit | Unscheduled Visit |
|---|-------------------|---|--|---|--|---|---|---|---------------|----------------------|
| | | | Visit 2 Dispense Lens 1 (3 - 4 days after Visit 1 [Washout period with habitual spectacles only after Visit 1]) | Visit 3 Week 1 Follow- up Lens 1 (7 -0/+1 days after Visit 2) | Visit 4 Week 2 Follow- up Lens 1 (7 -0/+1 days after Visit 3) | Visit 5 Dispense Lens 2 (2 [at least 48 hours] - 4 days after Visit 4 [Washout period with habitual spectacles only after Visit 4]) | Visit 6 Week 1 Follow- up Lens 2 (7 -0/+1 days after Visit 5) | Visit 7 Week 2 Follow- up Lens 2/Exit (7 -0/+1 days after Visit 6) | | |
| Informed Consent | | X | | | | | | | | |
| Demographics | | X | | | | | | | | |
| Medical History | | X | X | X | X | X | X | X | X | X |
| Concomitant Medications | | X | X | X | X | X | X | X | X | X |
| Inclusion/ Exclusion | | X | | | | | | | | |
| Habitual lens (brand, lens power*, lens care*) | | X | | | | | | | | |
| | | | | | | | | | | |
| Habitual Lens wear & Drop Usage* | | X | | | | | | | | |
| Keratometry (OD, OS) | | X | | | | | | | | |
| VA w/ habitual correction [†] (OD, | | X | | | | | | X | X | (X) |

| Procedure/ Assessment | Pre- screening | Visit 1 Screening/ Baseline/ Trial fit | Lens 1 (Period 1) | | | Lens 2 (Period 2) | | | Early Exit | Unscheduled Visit |
|--|-------------------|---|--|---|--|---|---|---|---------------|----------------------|
| | | | Visit 2 Dispense Lens 1 (3 - 4 days after Visit 1 [Washout period with habitual spectacles only after Visit 1]) | Visit 3 Week 1 Follow- up Lens 1 (7 -0/+1 days after Visit 2) | Visit 4 Week 2 Follow- up Lens 1 (7 -0/+1 days after Visit 3) | Visit 5 Dispense Lens 2 (2 [at least 48 hours] - 4 days after Visit 4 [Washout period with habitual spectacles only after Visit 4]) | Visit 6 Week 1 Follow- up Lens 2 (7 -0/+1 days after Visit 5) | Visit 7 Week 2 Follow- up Lens 2/Exit (7 -0/+1 days after Visit 6) | | |
| OS, logMAR distance)* | | | | | | | | | | |
| Manifest refraction* | | X | (X) | (X) | (X) | (X) | (X) | (X) | (X) | (X) |
| BCVA* (OD, OS, logMAR distance with manifest refraction) | | X | (X) | (X) | (X) | (X) | (X) | (X) | (X) | (X) |
| Biomicroscopy | | X | X | X | X | X | X | X | X | X |
| Randomization | | X | | | | | | | | |
| Fitting of investigational products (trial assessments): (Test and Comparator)* • VA (OD, OS, logMAR, distance) • Lens movement (overall fit- primary and peripheral gazes) • Lens position (centration; decentration – direction and amount) | | X | | | | | | | | |

| Procedure/ Assessment | Pre- screening | Visit 1 Screening/ Baseline/ Trial fit | Lens 1 (Period 1) | | | Lens 2 (Period 2) | | | Early Exit | Unscheduled Visit |
|--|-------------------|---|--|---|--|---|---|---|---------------|----------------------|
| | | | Visit 2 Dispense Lens 1 (3 - 4 days after Visit 1 [Washout period with habitual spectacles only after Visit 1]) | Visit 3 Week 1 Follow- up Lens 1 (7 -0/+1 days after Visit 2) | Visit 4 Week 2 Follow- up Lens 1 (7 -0/+1 days after Visit 3) | Visit 5 Dispense Lens 2 (2 [at least 48 hours] - 4 days after Visit 4 [Washout period with habitual spectacles only after Visit 4]) | Visit 6 Week 1 Follow- up Lens 2 (7 -0/+1 days after Visit 5) | Visit 7 Week 2 Follow- up Lens 2/Exit (7 -0/+1 days after Visit 6) | | |
| Study lens power to be dispensed | | X | | | | | | | | |
| | | | | | | | | | | |
| Dispense study lenses** | | | X | X | | X | X | | | (X) |
| Axis orientation at ██████████ ██████ 10 min after lens insertion | | | X | | | X | | | | |
| | | | | | | | | | | |

| | | | Lens 1 (Period 1) | | | Lens 2 (Period 2) | | | | |
|--------------------------|-------------------|---|--|---|---|---|---|---|---------------|----------------------|
| Procedure/ Assessment | Pre- screening | Visit 1 Screening/ Baseline/ Trial fit | Visit 2 Dispense Lens 1 (3 - 4 days after Visit 1 [Washout period with habitual spectacles only after Visit 1]) | Visit 3 Week 1 Follow- up Lens 1 (7 -0/+1 days after Visit 2) | Visit 4 Week 2 Follow- up Lens 1 (7 -0/+1 days after Visit 3) | Visit 5 Dispense Lens 2 (2 [at least 48 hours] - 4 days after Visit 4 [Washout period with habitual spectacles only after Visit 4]) | Visit 6 Week 1 Follow- up Lens 2 (7 -0/+1 days after Visit 5) | Visit 7 Week 2 Follow- up Lens 2/Exit (7 -0/+1 days after Visit 6) | Early Exit | Unscheduled Visit |

| | | | Lens 1 (Period 1) | | | Lens 2 (Period 2) | | | | |
|--------------------------|-------------------|---|--|---|--|---|---|---|---------------|----------------------|
| Procedure/ Assessment | Pre- screening | Visit 1 Screening/ Baseline/ Trial fit | Visit 2 Dispense Lens 1 (3 - 4 days after Visit 1 [Washout period with habitual spectacles only after Visit 1]) | Visit 3 Week 1 Follow- up Lens 1 (7 -0/+1 days after Visit 2) | Visit 4 Week 2 Follow- up Lens 1 (7 -0/+1 days after Visit 3) | Visit 5 Dispense Lens 2 (2 [at least 48 hours] - 4 days after Visit 4 [Washout period with habitual spectacles only after Visit 4]) | Visit 6 Week 1 Follow- up Lens 2 (7 -0/+1 days after Visit 5) | Visit 7 Week 2 Follow- up Lens 2/Exit (7 -0/+1 days after Visit 6) | Early Exit | Unscheduled Visit |
| | | | | | | | | | | |
| Lens wear calendar* | | | X | X | X | X | X | X | X | X |

| Procedure/ Assessment | Pre- screening | Visit 1 Screening/ Baseline/ Trial fit | Lens 1 (Period 1) | | | | Lens 2 (Period 2) | | | Early Exit | Unscheduled Visit |
|-------------------------------|-------------------|---|--|---|--|---|---|---|--|----------------------|----------------------|
| | | | Visit 2 Dispense Lens 1 (3 - 4 days after Visit 1 [Washout period with habitual spectacles only after Visit 1]) | Visit 3 Week 1 Follow- up Lens 1 (7 -0/+1 days after Visit 2) | Visit 4 Week 2 Follow- up Lens 1 (7 -0/+1 days after Visit 3) | Visit 5 Dispense Lens 2 (2 [at least 48 hours] - 4 days after Visit 4 [Washout period with habitual spectacles only after Visit 4]) | Visit 6 Week 1 Follow- up Lens 2 (7 -0/+1 days after Visit 5) | Visit 7 Week 2 Follow- up Lens 2/Exit (7 -0/+1 days after Visit 6) | | | |
| | | | (Dispense Calendar) | (Review Calenda r) | (Collect & Review Calendar) | (Dispense Calendar) | (Review Calendar) | (Collect & Review Calendar) | (Colle ct & Revie Calen dar) | (Review Calendar) | |
| Collect worn study lenses* | | | | X | X | | X | X | X | (X) | |
| | | | | | | | | | | | |
| AEs | | X | X | X | X | X | X | X | X | X | |
| Device deficiencies | | X | X | X | X | X | X | X | X | X | |
| Exit Form | | (X) | (X) | (X) | (X) | (X) | (X) | X | X | (X) | |

(X) Assessment performed as necessary, e.g., decrease of VA by 2 lines or more with investigational product (IP)

* Source only

+ Subject must have visual acuity with habitual correction of 0.30 logMAR (20/40) or better OU in order to leave the office
